1. What sustained molecular processes, activated by regular exercise, might be contributing to the maintenance or improvement of muscle mass in MHD subjects who participate in a 12 week exercise program? To this end, molecular events in the *resting* dominant limb of participants given placebo in regularly exercised (Group 1) and usual care (Group 3) subjects will be compared. We will test the postulate that regular exercise acts largely by inducing local changes in the expression of key regulators of muscle mass and also by stimulating the Akt/mTOR signaling pathways that serve to promote protein synthesis and inhibit proteolysis. We anticipate that a 12-week program of rehabilitation will increase muscle mass as measured by CT and DEXA scans, and improve skeletal muscle function via several interrelated mechanisms. These include changes in the balance between IGF-1 and myostatin, increased androgen receptor expression, changes in expression of components of the ubiquitin-proteasome and calpain proteolytic systems, suppression of inflammatory cytokines, and increased anabolic signaling. This is illustrated in Figure 3.

Figure 3. Assessment of 12 weeks of exercise training vs. usual care in resting muscle among subgroups receiving placebo.

2. What impact does acute exercise have on anabolic signaling in regular exercise versus usual care subjects? To answer this question we will measure activity (phosphorylation) of the IRS-1/AKT and mTOR signaling transduction pathways in the *acutely exercised* (and the contralateral resting) limbs of regular exercised subjects ingesting placebo (Group 1). The same measurements will be made in the muscle of the corresponding usual care group (Group 3) (Figure 4). Activity of the anabolic IRS-1/AKT and mTOR signaling pathways in the exercised limb will be compared with these responses in the contralateral resting limb of the same subject. We anticipate that acute exercise will activate anabolic signaling in both groups and that the response will be more vigorous in the regular exercise group.

[figure not shown]
Figure 4. Assessment of the response to acute exercise in trained vs. usual care subjects

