3. Does ingestion of a high-calorie leucine-rich protein (whey) supplement enhance acute exercise-stimulated anabolic signaling? (Specific Aim 2A). The effect of a nutritional supplement on acute exercise-induced signal transduction will be assessed by comparing IRS-1/AKT and mTOR signaling in a unilateral acutely exercised limb of regularly exercised subjects ingesting the supplement (Group 2) versus the acutely exercised limb of comparable subjects ingesting placebo (Group 1). A similar comparison will be made between the exercised limbs of usual care subjects ingesting the supplement (Group 4) versus placebo (Group 3) (Fig 5).

We anticipate that the leucine-rich supplement will enhance the acute exercise-stimulated mTOR signaling pathway and that the response will be more marked in the group undergoing the 12 week exercise program. This thesis is based on reports that in healthy young subjects, a leucine-rich supplement added to a resistance exercise program stimulates muscle protein synthesis, mass and strength (64; 72) and although delayed in the elderly, the anabolic response is effectively stimulated by this regimen (73). In this regard, Hulmi reported that whey protein enhanced exercise-induced signal transduction (phosphorylation of p70S6K) by nearly five-fold over exercise alone in young healthy subjects (71).

Figure 5. Assessment of the effect of nutrient supplementation on the response to acute exercise.

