In summary, we anticipate that a 12-week program of exercise rehabilitation will increase muscle mass and improve skeletal muscle function and that this is mediated by several different processes that we aim to identify. In this regard we expect that basal anabolic signaling will be higher in the resting muscle of the regular exercise group versus the resting muscle of the usual care group, *a potential carry over effect of regular exercise*. In addition, we anticipate that while the high calorie whey supplement will cause an increase in anabolic signaling in the resting muscle of both groups, the response will be greater in the regular exercise group, *again possibly reflecting a carryover effect of regular exercise*. *If a carryover effect is indeed present, then this would support the hypothesis that regular exercise is beneficial even in ESRD*. We also anticipate that acute exercise alone will increase anabolic signal transduction, and that this response will be enhanced by the high calorie whey supplement. If true, **this holds the prospect of developing a simple therapeutic strategy to boost the anabolic response to regular exercise and thereby enhance the functional and cardiopulmonary benefits of exercise in patients with ESRD**.

Detailed Protocol for Nutrient Supplementation, Acute Exercise, and Biopsy for Specific Aim 2. An outline illustrating the acute exercise, biopsy, and nutrient supplementation protocol for Specific Aim 2 is presented in Figure 2. On a morning the day before regular MHD and after an overnight rest, both regular exercise and usual care subjects will consume a light protein-free breakfast between 7 and 8 am and will be studied three hours later after a 60-min rest. Subjects in both groups will then begin a unilateral dominant lower limb exercise session lasting \approx 15 min, with the contra-lateral limb at rest. At the start of the exercise session, subjects will ingest half the high calorie whey or placebo so as to compensate for AA deficiencies common in MHD subjects. The other half of the supplement will be ingested at the end of the exercise session so as to enhance anabolic signal transduction. This will be followed by 60 minutes of rest, then muscle biopsies will be performed on both limbs to assess anabolic signal transduction.

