Statistical analysis plan. Comparisons of clinical and demographic data between groups at baseline will be performed by the appropriate statistical test (for continuous variables, t-test for normally distributed data and Wilcoxon test for non-normal data; for categorical variables, chi-square test or Fisher's exact test). These comparisons will be performed at baseline only to assess adequacy of randomization. Comparisons between groups for cardiopulmonary exercise test, muscle biopsy, energy expenditure, cognitive function, and other functional measures before and after the study period will be performed by multivariate ANOVA; post-hoc comparisons will be made using the Bonferroni method. To analyze continuous variables measured at three or more time points we will use linear mixed effects regression (114). To explore the relationships between a given outcome and other variables, we will use multiple regression techniques. Since the reliability of a fitted regression model may be reduced if too many predictors are used (114), we will limit the number of predictors to four variables in each model ($\leq 1/10$ of the total). For the primary outcome, change in peak VO_2 , the specific independent variables in the model will include exercise compliance (average energy expended in kcals/week), change in muscle strength, and change in muscle mass. Missing data will be managed using the multiple imputation method which is preferable to older methods and described in detail by Schafer & Olsen (1999).

For Specific Aim 2 (effect of acute and chronic exercise on muscle wasting), we will employ a linear model, using period (baseline vs. 4 months) and treatment (exercise training vs. usual care) as independent variables along with their interaction (Bonferroni method). The intention to treat principal will be applied for all analyses.

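### Specific Aim 2 predicts stronger acute-exercise and supplement responses in trained subjects, but the plan specifies no training-by-supplement test and leaves the trained v usual care test of the acute response unstated

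*Combined protocol and SAP*

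**What the plan says.** The approach to Specific Aim 2 makes three predictions that the arms will differ:

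- Question 2, acute exercise: "the response will be more vigorous in the regular exercise group".
- Question 3, supplement with acute exercise: "the response will be more marked in the group undergoing the 12 week exercise program".
- The summary after question 3, supplement in resting muscle: an increase in both arms, but "the response will be greater in the regular exercise group".

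The comparisons it states are these:

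- Question 2: signaling is measured in Groups 1 and 3 (both placebo), and activity "in the exercised limb will be compared with these responses in the contralateral resting limb of the same subject".
- Question 3: exercised limbs of "regularly exercised subjects ingesting the supplement (Group 2) versus the acutely exercised limb of comparable subjects ingesting placebo (Group 1"). Then: "A similar comparison will be made between the exercised limbs of usual care subjects ingesting the supplement (Group 4) versus placebo (Group 3").
- Secondary analyses, Specific Aim 2A: the change with exercise alone against exercise plus supplement, where change means exercised limb minus resting limb, and also supplement against placebo in the resting limb.
- Statistical analysis plan: a multivariate ANOVA for before-and-after comparisons between groups, muscle biopsy included, and for Specific Aim 2 a linear model "using period (baseline vs. 4 months) and treatment (exercise training vs. usual care) as independent variables along with their interaction".

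**The concern.** To say that trained subjects respond more is to make a claim about a difference between two differences. Testing the supplement in trained subjects, and then testing it again under usual care, does not estimate that quantity. If one test is significant and the other is not, the two effects may still be equal.

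The plan intends to build on this sub-study: the limitations section says that a positive pilot will form the basis of a more extensive study. With small cells and no stated between-arm contrast, a report could present a difference in significance as a difference in response, and a later trial could be designed around a training-dependent supplement effect that was never tested.

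**Working it through.** **Setting predictions against tests**

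| Prediction | Contrast needed | What the plan specifies |
|---|---|---|
| Question 2 | (exercised − resting limb), Group 1 v Group 3 | Exercised v resting limb within subject; the between-arm test is implied by the wording but not stated |
| Question 3 | (Group 2 − Group 1) − (Group 4 − Group 3) | Group 2 v 1 and Group 4 v 3, separately |
| Summary, resting muscle | The same difference of differences, resting limb | Supplement v placebo in the resting limb; no arm-by-supplement term |

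The interaction in the statistical analysis plan is period by treatment. It has no limb or supplement factor, and the acute session takes place once, after week 12, so it cannot test any of the three.

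**Checking the method on the plan's own figures.** For the primary endpoint (difference 17, SD 20, so 17/20 = 0.85; two-sided 0.05), the noncentral t gives power 0.805 at 23 per group and 0.786 at 22. The stated 23 is therefore reproduced. At 23 per group, effects of 0.3 and 0.5 give 0.169 and 0.382, against the stated 0.17 and 0.38. No power figure is given for Specific Aim 2A.

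**Inputs for the sub-study.** The documents give no SD for these responses, so effect sizes d (in SDs) are assumptions shown as a range. Two-sided 0.05 is carried over from the primary endpoint. The cell size is ambiguous: the 12 subjects from each group can mean 12 per cell (48 in all) or 12 per main arm, hence 6 per cell (24 in all). Both are shown.

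**Question 3, equal true supplement effect in both arms.** Let p be the power of one within-arm test (noncentral t, noncentrality d√(n/2), 2n − 2 df). The arms are independent, so exactly one is significant with probability 2p(1 − p), and trained only with probability p(1 − p).

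| d | n = 12: p | one arm only | trained only | n = 6: p | one arm only | trained only |
|---|---|---|---|---|---|---|
| 0.5 | 0.216 | 34% | 17% | 0.123 | 22% | 11% |
| 0.8 | 0.466 | 50% | 25% | 0.241 | 37% | 18% |
| 1.0 | 0.649 | 46% | 23% | 0.347 | 45% | 23% |
| 1.2 | 0.802 | 32% | 16% | 0.468 | 50% | 25% |
| 1.5 | 0.939 | 11% | 5.7% | 0.650 | 46% | 23% |
| 2.0 | 0.997 | 0.7% | 0.3% | 0.876 | 22% | 11% |

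In simulation (200,000 runs, d = 0.8), exactly one arm was significant in 49.7% of trials at 12 per cell and 36.6% at 6. The direct interaction test was falsely positive in 4.9% and 5.0%; half of the nominal 5%, or 2.5%, falls in the predicted direction.

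**Question 2, paired limbs in the two placebo cells, equal true effects.** With noncentrality d√n and n − 1 df, paired effects of 0.5, 0.8 and 1.0 give trained only in 23%, 20% and 10% of trials at 12 per cell, and 14%, 23% and 25% at 6.

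**What the direct tests can detect (80% power)**

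| Contrast | Standard error | 12 per cell | 6 per cell |
|---|---|---|---|
| Question 2, Group 1 v 3 | SD√(2/n) | 1.20 SD | 1.80 SD |
| Training-by-supplement interaction | SD√(4/n) = 2SD/√n, 4n − 4 df | 1.65 SD | 2.4 SD |
| Supplement averaged over both arms | SD/√n | 0.83 SD | 1.20 SD |

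Each SD is that of the outcome analysed; for question 2 it is the SD of the limb difference. If the supplement effect were 0.8 SD in trained subjects and half that under usual care, the interaction test would have about 10% power at 12 per cell and 8% at 6.

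**The case against.** The strongest reply is that the error is imputed. The plan never says that it will infer a difference from differing p-values, and it states no significance rule for the sub-study. All three differential statements are anticipations. That is right. A reader might infer that the plan commits to the fallacy; the documents show only that a valid test is missing.

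Question 2 is also closer to adequate than question 3. It asks about regular exercise against usual care, its Figure 4 caption says the same, and the power section defines a per-subject limb difference that could simply be compared between arms. The intention is visible; the test is not written. For question 3 the separate comparisons are explicit. The multivariate ANOVA does cover biopsy data between groups, but for before-and-after comparisons and with no limb or supplement factor.

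A reader might also connect these comparisons to the carry-over effect that the summary says would support a benefit of regular exercise. That passage concerns resting muscle. Basal carry-over is tested directly by question 1 (Group 1 v Group 3); only the resting-limb supplement prediction lacks its contrast.

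The error rates depend on d. At 12 per cell they become small for large effects, and the plan cites a nearly five-fold enhancement in young healthy subjects, so large d cannot be excluded. At 6 per cell they remain at 11% even for d = 2.0.

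Finally, this is a declared pilot without a power analysis, and Hypothesis 2A asks whether the supplement enhances the response, not whether it does so more in trained subjects. That excuses low power and limits the severity. It does not supply the contrast for predictions that the plan chose to make.

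**Conclusion.** The concern holds as an omission. For the supplement, in the exercised and the resting limb, the plan predicts a larger response in trained subjects but contains no training-by-supplement term. For acute exercise, the between-arm comparison is implied but not specified.

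If significance in one arm alone were taken as a difference, the predicted but false result would appear in about 16-25% of trials at 12 per cell and 11-25% at 6, for d of 0.5-1.2, against 2.5% for a direct test. These figures rest on equal true effects, a two-sided 0.05 level and assumed effect sizes. They apply per signaling protein.

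The direct test will itself have little power, so any differential finding can only be exploratory. The primary endpoint is unaffected. The change is worth making because it uses data already planned.

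**What to change.** Under questions 2 and 3, the summary that follows them, and the statistical analysis plan, specify for each signaling protein:

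1. **Question 2:** the exercised-minus-resting difference compared between Groups 1 and 3, placebo subjects only.
2. **Question 3:** the interaction (Group 2 − Group 1) − (Group 4 − Group 3) on one named outcome. First reconcile question 3, which uses the exercised limb, with the power section, which uses exercised minus resting limb.
3. **Resting-muscle prediction:** the same interaction in the resting limb. An interaction on the limb difference would not serve, because it subtracts the resting limb out.

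Report each estimate with its confidence interval as exploratory. Claim a larger response in trained subjects only from these estimates; otherwise report the supplement effect averaged over both arms. Reconcile the cell size, and state the detectable interaction in SDs of the analysed outcome: about 1.65 at 12 per cell, 2.4 at 6.

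The cost is wording and a few model terms, with no new data or visits. The downside is that the stated ability to show a differential response becomes less favourable.

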There has been intense interest in establishing whether the anabolic response to exercise can be enhanced by providing supplemental EAA (64-66). In normals, leucine-rich supplements are especially effective in promoting muscle protein synthesis and when combined with resistance exercise cause an even greater increase in muscle protein synthesis than exercise alone (64; 67). A similar response is seen with endurance exercise (68). Among commonly used protein supplements, whey is of special interest. It is readily digestible, is rich in EAA (~50g/100g/protein), particularly leucine (14g/100g), has a low Na, K, and phosphorus content, is inexpensive, and is effective in enhancing muscle protein synthesis (66; 69; 70). Hulmi (71) reported that whey acutely increased anabolic signaling in resistance exercise-trained normal subjects over 10.5 weeks. Regular exercise with whey supplementation caused a greater increase in muscle mass than exercise alone. Commonly a carbohydrate is added to the whey or AA supplement to stimulate insulin release and inhibit proteolysis induced by exercise (72). This combination also stimulates anabolic signaling induced by endurance exercise (68). Since in ESRD alterations in serum and intracellular AA profile with reduced serum BCAA levels are common (17; 23), provision of EAA at the time of exercise is likely to be especially effective. However, it is conceivable that there may be resistance to the signaling response to AA as there is for insulin/IGF-1 in CKD (50; 58). In healthy elderly subjects there is some impairment to AA-induced protein synthesis (73), and this can be overcome by increasing the leucine load (66), particularly in the form of whey protein (74). In a study with CKD rats, described below, we found that leucine alone largely corrects and stimulates the anabolic signaling defect present in these rats (30). Since leucine also stimulates protein synthesis in non-exercising humans including the elderly, it is recommended that the diet of the elderly include leucine-rich foods to prevent and treat sarcopenia (6; 75).

Specific Aims:

Specific Aim 1. To devise a safe, low-cost aerobic and resistance exercise regimen to counteract the loss of muscle mass and function common in elderly MHD patients that is easily implemented, suitable for the home and to which most subjects will adhere.

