General study design: MHD subjects aged 65-80 years with impaired exercise capacity and function will be randomized into two groups (30/group). One group will undergo a home-based exercise program and the other usual care over a 12 week period. This subject number allows for a drop-out rate of 20%, while maintaining 80% power to detect a significant difference in our primary end-point, peak VO_2 . After enrollment, all subjects will be encouraged to consume at least 1.2 g/kg/protein/day throughout the study. The 12-week program will include a 2-week clinic-based exercise instruction period with testing at baseline before intervention and after 6 and 12 weeks. Measures at baseline and 12 weeks will include body composition by anthropometrics and dual energy X-ray absorptiometry (DEXA), thigh muscle volume and composition by CT scan, muscle strength and function, cardiopulmonary exercise testing, QOL, cognitive function and nutritional, inflammatory, lipid and biochemical status. Muscle biopsies will be obtained at baseline and at 12 weeks and will be assayed for signaling proteins, and gene and protein expression of key muscle mass regulators. More limited interim testing will be performed at 6 weeks. In addition, two to three days after the 12-week study, a pilot sub-study will be performed to test whether a high-calorie leucine-rich protein supplement enhances exercise-stimulated anabolic signaling. At this time muscle biopsies will be taken. Overviews of the study measurements and timeline are presented in Appendices I and II.

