The unilateral exercise will be performed using seated single knee extension exercise against resistance. Subjects will be seated with the hips flexed at 90° with their back against a backrest at a ≈110° angle. The leg pad will be positioned ≈5 cm above the ankle and the rotation arm will be positioned so that the knee is bent to 90°. After a warm-up consisting of 8-10 repetitions with minimal resistance, the weight will be adjusted to 70% of the one repetition maximum. The unilateral 1-RM will be determined by a post-training period strength test, performed on a different day. Five sets of 10 repetitions will be performed, with 2 minutes of rest periods between sets. The load will be adjusted during the course of the session due to fatigue such that each subject is able to perform 10 repetitions during each set.

The supplement, high-calorie whey, (300 ml) comprises 24 g whey protein (contains ≈3 g leucine) with 30g carbohydrates (sucrose) in liquid, and the placebo contains a liquid, dextrose 24 g plus sucrose 30g. The amount of whey (Nestle Healthcare) prescribed is guided by studies in normal subjects (66; 69; 70; 110) including the elderly (70; 74). We do not anticipate any adverse effects from nutrient or placebo if taken as prescribed. Whey has a low NA, K and phosphorus content (60,140 and 60 mg/serving respectively). The vehicle for dissolving the powdered supplement will be of the subject's choice, but is limited to fluids permissible for ESRD such as apple juice and will be pre-tested for taste by the subject. Whey is also available in a variety of flavors and in long term studies has been included in baked goods or sprinkled over foods.

Detailed molecular analysis of skeletal muscle. The following items will be measured using methods established in [name] laboratory. Note that receptor and signaling proteins will be measured by western immunoblots; mRNA levels by real-time quantitative PCR, and selected degradative proteins by immunoblotting and serum and local IGF-1 by ELISA.

- mRNA levels of local regulators of muscle mass: Total IGF-1 (all transcripts), the Ea transcript (a generalized tissue form and main form in liver, and the IGF-1Eb transcript, MGF, a loading sensitive and more potent form than the Ea form). Myostatin, and receptors for IGF-1, insulin, growth hormone and androgens.
- mRNA levels of inflammatory cytokines IL-6 and TNF α .

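### The resting-limb samples labelled basal are taken 60 to 75 minutes after at least 54 g of sugar, so for phospho-proteins they cannot separate higher unstimulated signaling from a larger response to the drink

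*Combined protocol and SAP*

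**What the plan says.** Under B. Approach to Specific Aim 2, question 1 asks: "What sustained molecular processes, activated by regular exercise, might be contributing to the maintenance or improvement of muscle mass". It is answered by comparing resting-limb muscle of trained and usual-care subjects who received placebo (Group 1 v Group 3). The summary that follows the three questions states: "we expect that basal anabolic signaling will be higher in the resting muscle of the regular exercise group". It calls this a potential carry-over effect and says that, if present, it would support a benefit of regular exercise in ESRD.

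The Detailed Protocol for Nutrient Supplementation, Acute Exercise, and Biopsy sets the sampling conditions. "At the start of the exercise session, subjects will ingest half the high calorie whey or placebo"; the other half follows at the end of about 15 minutes of one-leg exercise. Then: "This will be followed by 60 minutes of rest, then muscle biopsies will be performed on both limbs". On composition, "the placebo contains a liquid, dextrose 24 g plus sucrose 30g". The subject chooses the vehicle, "limited to fluids permissible for ESRD such as apple juice".

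Each limb is biopsied once in the sub-study. The General study design also says: "Muscle biopsies will be obtained at baseline and at 12 weeks". Neither that section nor the biopsy procedure under Muscle biopsy measurements states the feeding conditions of those samples.

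**The concern.** A sample taken about an hour after a sugar drink is not unstimulated. The protocol supplies each link of an alternative explanation:

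- The Background section says: "Commonly a carbohydrate is added to the whey or AA supplement to stimulate insulin release".
- The Figure 1 legend and the list of molecular assays name insulin as an activator of the proteins being measured.
- The section on insulin sensitivity under Biochemical tests expects training to improve it.

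If all three hold, trained and usual-care subjects could have the same unstimulated signaling and still differ in phosphorylated IRS-1, Akt, mTOR, p70S6K, rpS6 and 4EBP-1 when sampled. Giving both groups the same drink does not remove a difference in how strongly they respond to it.

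At stake is one mechanistic conclusion: whether a Group 1 v Group 3 difference shows a lasting change in resting muscle or a better acute response to carbohydrate. The listed limitations do not raise the point.

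**Working it through.** **Dose and timing (from the detailed protocol)**

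- Sugar in the placebo: 24 g dextrose + 30 g sucrose = 54 g. Any sugar in the vehicle is extra, so 54 g is a minimum.
- First half to biopsy: about 15 min exercise + 60 min rest = about 75 min.
- Second half to biopsy: 60 min.
- There is one biopsy per limb, so no pre-drink resting sample that day. No insulin or glucose measurement is described at the biopsy; the HOMA-IR samples are fasting, at weeks 0, 6 and 12.

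**What the comparison measures**

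Set unstimulated signaling to 1 in both arms. Let the drink raise it k-fold in usual care, and let training enlarge the rise by a fraction f. Then:

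- usual care at biopsy = k
- trained at biopsy = 1 + (k − 1)(1 + f)
- difference = f(k − 1) in units of the unstimulated level
- relative difference as observed = f(k − 1)/k

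The documents give neither f nor k; the values below are assumptions.

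| f | k | usual care | trained | relative difference |
|---|---|---|---|---|
| 0 | 2 | 2.0 | 2.0 | 0% |
| 0.1 | 2 | 2.0 | 2.1 | 5% |
| 0.2 | 2 | 2.0 | 2.2 | 10% |
| 0.2 | 3 | 3.0 | 3.4 | 13% |

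Since (k − 1)/k is below 1, the relative difference produced this way is always smaller than f.

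**Chance of a significant result with no unstimulated difference**

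The plan gives no variance for these measures and no power analysis for signaling, so the difference is expressed as an assumed d in standard deviations. Thirty per arm less 20% dropout leaves 24, half of whom receive placebo: 12 per cell. For a two-sided 5% t-test the noncentrality is d√(12/2) on 22 degrees of freedom. The three sizes are those the plan calls small, medium and large.

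| d | noncentrality | probability of significance, 12 per cell | same, 6 per cell |
|---|---|---|---|
| 0 | 0 | 0.05 | 0.05 |
| 0.3 | 0.73 | 0.11 | 0.08 |
| 0.5 | 1.22 | 0.22 | 0.12 |
| 0.8 | 1.96 | 0.47 | 0.24 |

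The last column covers the case where 12 is read as the number per training arm rather than per cell.

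**Whether other samples settle it**

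The General study design assays baseline and 12-week biopsies for signaling proteins, and the Statistical analysis plan has a period-by-treatment model for Aim 2. Whether the 12-week sample is separate from the sub-study biopsy is unclear. Specific Aim 1 places biopsies after the 12 weeks, and the secondary analysis for Specific Aim 2 uses resting-limb muscle with 12 per group, which may be the sub-study sample. If so, and if baseline was taken without the drink, the change from baseline mixes training with feeding.

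One wording conflict also needs reconciling. Question 1 names the dominant limb as the resting one, while the description of the biopsies and the detailed protocol exercise the dominant limb and rest the other.

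**The case against.** The strongest reply is that training was randomised and Groups 1 and 3 receive the same placebo. A difference between them is therefore an effect of training, and a better insulin response is itself a benefit. The summary also uses carry-over broadly: it applies the term to a larger resting-muscle response to whey in trained subjects. This stands. A reader might infer that the comparison is biased or that any difference would be spurious; the documents do not support that. What it does not rescue is the narrower description of the difference as basal or sustained.

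A reader might also infer that trained subjects would necessarily show more signaling. The protocol cites a recent MHD study in which aerobic exercise gave no insulin-sensitivity benefit, and describes insulin signaling as impaired in CKD. Only *could* is justified.

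Three further readings go too far.

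- In the example with f = 0.2 and k = 2, the 0.2 is 20% of the pre-drink level, but the samples compared are post-drink, where it is 10%.
- Free choice of vehicle does not bias the comparison, since no reason is given for choices to differ by arm. It mainly adds noise.
- The acute-exercise contrast is much less exposed, because it compares exercised with resting limb in the same subject and both share the drink. The sugar placebo is also a sensible comparator for whey in question 3.

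Much of question 1 concerns mRNA and protein expression rather than phosphorylation. Figure 2, which outlines the procedure, is not available here, so inferences from silence need caution.

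**Conclusion.** The point holds in limited form. The Group 1 v Group 3 resting-limb comparison validly estimates the effect of training on carbohydrate-fed resting signaling. For phospho-proteins it does not identify unstimulated signaling, so the labels basal and sustained are not supported by that sample.

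The size cannot be derived from the documents. It is zero if training does not change the insulin response. Otherwise, in the simple model above, it is less than the fractional gain in that response. The argument rests on the protocol's own statements about carbohydrate, insulin and training, and on the stated 54 g and 60 to 75 minutes. That mRNA, total protein, DNA and RNA content are less likely to respond within about an hour is a working assumption; the documents do not address it.

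This is a pilot secondary aim. The peak VO2 comparison and its sample size are untouched.

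**What to change.** 1. In question 1 and the Aim 2 summary, report the Group 1 v Group 3 phospho-protein result as *post-carbohydrate resting signaling*. Limit the basal and sustained conclusion to mRNA, total protein, DNA and RNA content, and state the assumption behind that choice. Add the point to the limitations.
2. State whether the 12-week biopsy is a separate sample and under what conditions it and the baseline biopsy are taken. If it is separate, and both are rested and pre-drink, use that change from baseline for basal phospho-signaling. If not, do not add a biopsy, and do not treat an unfed baseline and a post-drink end sample as like for like.
3. Use one identical permitted vehicle for all sub-study subjects and record its sugar content, to remove avoidable variation in the load.
4. Reconcile which limb is the resting one.

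None of this adds a biopsy or a visit. Items 1, 2 and 4 are wording and can be settled even after samples are collected; item 3 must be in place before sub-study testing. The price is a narrower phospho-protein claim and less choice of taste for subjects.
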